discharge. Because the attachment feature of SM was not available at the time of the pilot, we instead used a text-based format, embedded in the body of the SM (figure 1 in Appendix 2), for the pharmacist and Veteran to reconcile medications. As we will do in the proposed SMMRT Trial, we recruited hospitalized Veterans, registered them for MHV, and trained them to use MHV and SMMRT. After discharge, our pharmacist reviewed the CPRS records of 51 eligible Veterans and identified 108 clinically important medication discrepancies (median 2 per Veteran), mostly medications that the Veteran was taking but were omitted from the

discharge summary or discharge medication list. After correcting these discrepancies, the pharmacist sent SMMRT via SM to the Veteran. A total of 34 Veterans (67%) returned SMMRT. Of these 34 Veterans, 17 (50%) had additional discrepancies, most commonly duplicative medications prescribed for the Veteran at VA Boston and another VA facility. Nine of 10 Veterans completing post-intervention in-depth interviews (similar to those proposed in Aim 3) said they would use SMMRT again. Appendix 5 presents direct quotes about SMMRT from these Veteran participants. This study demonstrated the feasibility of recruiting hospitalized Veterans and training them in MHV and SM. Results highlighted the high prevalence of medication discrepancies immediately after discharge and the ability to detect and correct them by SMMRT.

#Aligning Medication Reconciliation and SM: A Qualitative Study of Providers' Perspectives.

In this study, published in *JMIR*,³⁹ we conducted in-depth interviews with 15 primary care providers to characterize ambulatory medication reconciliation, the use of SM in primary care, and perceptions of a SMMRT-like medication reconciliation system. Providers recognized the value of medication reconciliation, especially after hospital discharge, and suggested numerous challenges to medication reconciliation. Providers emphasized the importance of collaborating with pharmacists in reviewing Veterans' medication regimens.

#Qualitative Study of Pharmacists' Role in Medication Review and Reconciliation.

[name] recently completed a series of interviews with clinical pharmacists regarding their role in medication management. Preliminary analyses revealed considerable enthusiasm among pharmacists for developing relationships and monitoring patients to improve medication safety.

#Medication Discrepancies.

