We propose a two-arm RCT, with 120 participants in each arm. The main outcome measure will be combined number of medium- and high-significance medication discrepancies present at the 30-day follow-up. Conservative estimates suggest that we would expect a rate of 3.0 medium- or high-significance medication discrepancies per patient in the Usual Care group. Using a custom simulation, with two-tailed alpha error set at 5%, we calculated that this sample size (120 subjects per arm) would have 99.9% power to detect a lowering of the rate from 3.0 to 2.0 and 82% power to detect a lowering of the rate from 3.0 to 2.4.

6. Measures.

Study measures will be derived from baseline and 1-month follow-up interviews, as well as from CPRS.

Predictor Variable. The predictor variable will be the experimental condition (i.e., Usual Care SMMRT), assigned by random allocation (see above).

Main Outcome Variable. The primary outcome measure will be medication discrepancies detected 30 days after discharge. Secondary outcome measures will be 30-day hospital utilization (combined readmissions plus emergency department use) and Veterans' self-efficacy in medication use.

Secondary Outcome Variables. Secondary endpoints, ascertained through a combination of CPRS review

plus follow-up interview with participants, include community tenure (days spent outside of the hospital), medication discrepancies (overall and by subtype, i.e., omissions, commissions, duplications, and alterations in dose or frequency); health status (SF-12 health status scale; 12 items, 2-3 minutes), medication use self-efficacy (score of 0 to 8, based on validated 8-item yes/no MUSE scale;⁶² 3 minutes); and the Care Transition Measure (score of 0 to 100, based on validated 15-item, 4-point [strongly agree, agree, disagree, strongly disagree] scale, linear transformed to 0 to 100 scale,⁶³ 5 minutes).

Other Variables. Prior to randomization, we will stratify participants on the basis of My HealtheVet in-person authentication status (yes/no) and VA Boston primary care (yes/no); see above Figure 2 and Section 4.e.5. Baseline data will include age, educational level, race/ethnicity. At baseline, we will administer the 7-item REALM-SF health literacy scale,⁶⁴ the SF-12, and the medication use self-efficacy scale (MUSE). During the 30-day follow-up we will re-administer the SF-12, the CARE Transition measure and the MUSE.

7. Statistical Analysis.

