Preliminary Analyses. In preliminary analyses, descriptive statistics and bivariate associations will be computed. Then we will assess whether there are differences between the study arms for socio-demographic variables. We will assess imbalance formally using Analysis of Variance for continuous variables and Chi Square tests for dichotomous variables. In order to confound any observed effect of the treatment, a covariate must be imbalanced between the arms and also associated with the outcome. Thus, we will judge how plausible confounding is based on the formal tests, the degree of imbalance, and the plausibility of association with the outcome. Primary analysis will not include any potential confounders, but sensitivity analyses will adjust for plausible confounding variables with large imbalance between the arms.

Statistical Analyses. The primary hypothesis is that SMMRT will result in a reduction in 30-day medication discrepancies as compared with UC. The main outcome will be tested by a two-step analysis. First, we will conduct a logistic regression to compare SMMRT vs. UC. We will take an intent-to-treat approach to the analysis; Veterans will be included in our primary analyses regardless of their level of adherence with their assigned intervention. For participants who do not complete the telephone assessment, we will rely on CPRS/CDW data for outcome assessment.

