Checks and treatment for “non-Response” Bias. The potential for differential drop-out rates among the three groups is itself an interesting and important empirical question, with clinical implications. Drop outs will be defined as active drop outs (Veterans who request discontinuation of participation) and passive drop outs (Veterans who cannot be reached for follow-up within 60 days of discharge). Factors that may contribute to drop-out rate will be tested by logistic regression. This logistic regression will be used to generate completion probabilities, which we will use as Inverse Probability Weights (IPWs). We will then use the IPWs in a weighted logistic regression for the outcome as predicted by study arm. Heuristically, Veterans with low probabilities of response who do respond are upweighted to represent Veterans who did not respond. Veterans who were quite likely to respond will not be upweighted as much. The result is a weighted sample that resembles the original population. In the weighted analysis, we will use the robust or “sandwich” variance estimator to account for the variability added by estimating the IPWs.

Methods for Aim 2: In-Depth Interviews

Aim 2 . To evaluate MHV training and SMMRT interventions for potential future implementation. For this formative evaluation, we will use qualitative research methods to examine in-depth how Veterans perceived their interactions with the MHV Training and SMMRT intervention components. *We will also interview PACT RNs and Pharmacists to solicit their perspective on the integration of SMMRT into the post-discharge PACT workflow and will analyze related information collected from chart abstraction.*

Rationale for formative evaluation.

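### The primary outcome is a count powered as a rate, but the only test named is logistic regression with no event defined, so the stated 82% power does not belong to that test

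*Combined protocol and SAP*

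**What the plan says.** All references are to the combined protocol and SAP, section (4) Work Proposed, Methods for Aim 1.

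- **Item 5, Sample size and power**, sets the design ("We propose a two-arm RCT, with 120 participants in each arm") and the outcome: "The main outcome measure will be combined number of medium- and high-significance medication discrepancies present at the 30-day follow-up". The control assumption is a mean: "we would expect a rate of 3.0 medium- or high-significance medication discrepancies per patient in the Usual Care group". Power comes from an undescribed simulation ("Using a custom simulation, with two-tailed alpha error set at 5" per cent). It is given as 99.9% for 3.0 versus 2.0 and, for the smaller effect, as "82% power to detect a lowering of the rate from 3.0 to 2.4". Neither the simulated distribution nor the simulated test is named.
- **Item 6, Measures**, repeats that the primary outcome is 30-day discrepancies and adds no cut-point.
- **Item 7, Statistical Analyses**, names the test: "The main outcome will be tested by a two-step analysis. First, we will conduct a logistic regression to compare SMMRT vs. UC". The text then turns to intention to treat and missing interviews. The primary analysis carries no potential confounders.
- **Item 7, non-response bias**, returns to the same kind of model: "We will then use the IPWs in a weighted logistic regression for the outcome as predicted by study arm". Again no event is given.

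The analysis of variance and chi-square tests in item 7 are for baseline imbalance only.

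**The concern.** Binary logistic regression needs a binary outcome, and the plan defines a count. Someone must decide whether the event is any discrepancy, three or more, four or more, or something else, and must also decide what the second step is. Nothing in the plan prevents those decisions from being made after the data are seen.

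The weighted logistic regression for non-response could be read as step two. It is not labelled so, it also lacks an event, and the plan does not say which step decides the result.

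At stake are the form of the single confirmatory test and the justification for 240 patients. Cutting a count at one point discards information, and how much is lost depends on the cut and on how the intervention works.

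**Working it through.** **Inputs.** From item 5: 120 per arm, two-sided 5%, means 3.0 versus 2.4 (stated power 82%) and 3.0 versus 2.0 (stated 99.9%). The documents give no variance or distribution, so each case below is an assumption. No attrition is applied.

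**Step 1: reproduce the stated power as a count comparison.** With Poisson variance, expected totals are 120 × 3.0 = 360, 120 × 2.4 = 288 and 120 × 2.0 = 240.

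- 3.0 versus 2.4: z = ln(3.0/2.4) / √(1/360 + 1/288) = 0.2231/0.0791 = 2.82. Power = Φ(2.82 − 1.96) = 80.6%. Poisson regression with robust variance, 40,000 simulations, gives 80.7%.
- 3.0 versus 2.0: z = ln(1.5) / √(1/360 + 1/240) = 0.4055/0.0833 = 4.87. Power = 99.8%.

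Both lie within 2 points of the stated figures, so those figures fit a count comparison. This does not prove what was simulated.

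**Step 2: power of the named test, both arms Poisson (case A, 3.0 versus 2.4).** Without covariates, logistic regression on arm is a comparison of two proportions. For each cut c, p = P(Poisson ≥ c). Power is by exact enumeration of all 121 × 121 tables, and ranges run from the Wald to the likelihood-ratio test. The N per arm for 82% power is [1/(p0q0) + 1/(p1q1)] × (2.875/ln OR)², with 2.875 = 1.960 + 0.915.

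| Event | Usual care | SMMRT | Power, 120 per arm | N per arm for 82% |
|---|---|---|---|---|
| ≥1 | 95.0% | 90.9% | 21–25% | 663 |
| ≥2 | 80.1% | 69.2% | 49–50% | 265 |
| ≥3 | 57.7% | 43.0% | 61% | 194 |
| ≥4 | 35.3% | 22.1% | 62% | 198 |
| ≥5 | 18.5% | 9.6% | 50–53% | 261 |

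Worked example for ≥3: 1/(0.5768 × 0.4232) + 1/(0.4303 × 0.5697) = 8.18; ln OR = 0.590; 8.18 × (2.875/0.590)² ≈ 194. Cuts above 5 do worse.

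**Step 3: the larger effect (case B, 3.0 versus 2.0).** Any versus none gives 62–66%. The best cut, ≥3, gives 98%.

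**Step 4: other effect patterns with the same mean of 2.4.**

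- *Case C.* The effect is confined to a share equal to the pilot's return rate (section (3), pilot study: "A total of 34 Veterans (67%) returned SMMRT"). Those patients have mean 3.0 × (1 − 0.2985) and the rest 3.0; overall 3.0 × (1 − 0.67 × 0.2985) = 2.4. Count 80%; ≥1 27–31%; ≥3 63–64% (best cut); ≥4 59–60%.
- *Case D.* SMMRT clears every discrepancy in 20% of patients and does nothing in the rest: 0.8 × 3.0 = 2.4. Any versus none is now 95.0% versus 0.8 × 95.0% = 76.0%, and power is 99%. The others are ≥2 80%; ≥3 42%; ≥4 21–22%; ≥5 11–12%. The robust count comparison has about 70%.

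**Step 5: overdispersion.** Assume a negative binomial with variance μ + kμ². Count power is Φ(0.2231/√[(1/3.0 + 1/2.4 + 2k)/120] − 1.96). Best-cut power uses the usual two-proportion approximation.

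| k | Count model | Best single cut |
|---|---|---|
| 0.1 | 71% | 52% |
| 0.2 | 63% | 45% |
| 0.5 | 46% | 32% |

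**The case against.** The strongest reply is that the power loss is conditional. Logistic regression need not mean one dichotomy: an ordinal logistic model uses the whole count, and a rank test, its near analogue, had about 78% power in simulation for 3.0 versus 2.4 under Poisson. The unwritten second step might also be a count model. Both points are fair, but the plan says neither ordinal nor count, so they show how much is left open rather than closing it.

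Other points stand and limit the numbers:

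- The larger planned effect is well covered if the cut is well chosen.
- Dichotomising can win: in case D, any versus none beats the count model. A predefined binary outcome is therefore a legitimate choice.
- Case C is only an illustration. In the pilot, and in the planned intervention, the pharmacist reconciles the record before sending the message, so Veterans who never reply may also benefit.
- No passage supports the all-or-none pattern of case D.
- Naming a count model does not by itself secure 82%, as the overdispersion figures show.

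**Conclusion.** The concern holds and must be fixed before outcome data are analysed. The firm part needs no distributional assumption: the plan powers a count, names only logistic regression, defines no event, and announces a two-step test with one labelled step.

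The size is conditional. Under Poisson counts, which come within 2 points of the plan's own power, the best single cut loses about 20 points for the smaller effect (about 62% against 82%). Any versus none loses about 57 to 61 points. Across cases A and D, cuts from ≥1 to ≥4 give from about 21% to 99% power for the same fall in mean. Which event is best therefore cannot be settled without stating how the effect is expected to arise.

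**What to change.** Make the deciding test match the powered outcome. Suggested text for item 7:

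> The number of medium- plus high-significance discrepancies at 30 days will be compared between arms by one log-link count regression (Poisson with robust variance), without potential confounders. The rate ratio with its 95% confidence interval, at two-sided 5%, decides the primary result.

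Then:

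- Use the same model, weighted, in the non-response analysis, which already plans a sandwich variance.
- Write out step two or delete the reference to two steps, and say which step decides. If the weighted analysis is step two, label it.
- Make any logistic analysis secondary, with its event defined.
- In item 5, state the model and dispersion assumed in the simulation, and restate the power for the chosen test.

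A binary primary outcome would also resolve the mismatch, provided its event is fixed in advance and the power is restated for it.

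The cost is SAP wording and one rerun of the simulation. No new data or staff are needed; more patients are needed only if the restated power is judged too low.

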- Thank you for allowing me the chance to tell you about our study. I would like to ask you a few questions first to see if you meet the requirements for eligibility. Would that be okay?

[figure not shown]
1. **Do you have access to a computer? Y/N** (*If yes, continue. If no skip to question 4*)
2. **Do you use a computer to connect to the internet, say to search websites or for email?**
3. ***If yes, Do you use secure messaging? If no, would you be willing to use it if required for this study?***
4. **Does anyone help you manage your medicines? Y/ N** (*If yes, continue. If no, not eligible, go to Verbal consent*)
5. **Does that person use a computer/ internet/ email? Y/N** (*If yes, continue. If no, not eligible, *Would you be willing to have your caregiver use secure messaging on your behalf if required for this study?**

If no to either 2 or 3: Unfortunately, you do not meet the criteria to participate in this study. Thank you for your time and interest.

→If Yes to 3 and 4, administer the Callahan screener. If patient passes the screener, then the patient is eligible. Continue on to ICF and HIPAA forms.

3. Randomization and intervention

Veterans successfully recruited and consented to participate will be randomly allocated to either UC or UC+SMMRT. Veterans randomized to UC+SMMRT will receive introduction to My HealtheVet and SMMRT. Within 3 business days of discharge, the SMMRT Research Pharmacist will engage with Veterans and/or their designated family members to conduct medication review and reconciliation via Secure Messaging. See randomization scheme below.

After baseline assessment is complete, participants will be randomly assigned via computer program to receive 1) usual care or 2) UC plus pharmacist-mediated medication reconciliation (SMMRT). After opening, the research assistant will inform the Veteran of the “treatment assignment.”

Overview of the Intervention

[figure not shown]
The intervention principally entails the creation of a personalized medication list for each Veteran/subject, incorporating most current data from Vista (the medical record) into a user-friendly PDF-file interface, i.e. the SMMRT. The research pharmacist will send the SMMRT via attachment to Secure Message to the Veteran and will then interact with the Veteran to ensure that the medical record accurately reflects what medications the Veteran is taking.

What Happens in the Intervention?

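### The outcome models name neither the two stated randomisation strata nor the baseline MUSE and SF-12 scores, and the protocol gives two orders for baseline and randomisation

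*Combined protocol and SAP*

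**What the plan says.** All references are to the combined protocol and SAP, Methods for Aim 1, unless stated.

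- **Strata.** Section 6, Measures (Other Variables), says that before randomisation "we will stratify participants on the basis of My HealtheVet in-person authentication status (yes/no) and VA Boston primary care (yes/no"). Section 3, Randomization and intervention, does not mention strata. A figure there is not shown in the supplied text.
- **Outcome models.** Section 7, Statistical Analysis, describes two. The primary one is "First, we will conduct a logistic regression to compare SMMRT vs. UC", given as the first step of a two-step analysis whose second step is not clearly identified. The other, for non-response, is "We will then use the IPWs in a weighted logistic regression for the outcome as predicted by study arm". The Preliminary Analyses paragraph keeps potential confounders out of the primary analysis and allows sensitivity adjustment for plausible confounders that are markedly imbalanced.
- **Baseline scores.** Section 6 lists among the baseline instruments "the SF-12, and the medication use self-efficacy scale (MUSE"), and adds "During the 30-day follow-up we will re-administer the SF-12, the CARE Transition measure and the MUSE". MUSE self-efficacy is one of the two secondary outcomes named first. Section 7 gives no model for any secondary endpoint.
- **Order of events.** Section 3: "After baseline assessment is complete, participants will be randomly assigned via computer program". The same paragraph continues "After opening, the research assistant will inform the Veteran of the" assignment. The Aim 1 text in (5) Human Subjects names randomisation first and the baseline interview after it.

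**The concern.** If allocation is stratified, the usual practice is to carry the strata into the analysis. Otherwise the reported standard error ignores the balance that the design created, and the test is somewhat conservative when the strata are prognostic. The sensitivity route is unlikely to reach these two factors, because it is triggered by large imbalance and stratification exists to prevent that.

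For MUSE and SF-12, the baseline value is usually the strongest available predictor of the 30-day value. With no model stated, the choice among 30-day score alone, change score and baseline-adjusted score stays open until the data are seen, and these can differ widely in power.

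The order of events matters because both scores are self-reported. If the interview follows randomisation and the Veteran has been told the arm, the answers may reflect that knowledge, and the score is no longer a clean baseline to adjust for.

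**Working it through.** **1. The plan's own figure.** Inputs from Section 5: 120 per arm, two-sided 5%, rates 3.0 and 2.4, "82% power to detect a lowering of the rate from 3.0 to 2.4". For an unadjusted Poisson comparison, SE = √(3.0/120 + 2.4/120) = 0.212, and power = Φ(0.6/0.212 − 1.96) = Φ(0.87) = 80.7%. For 3.0 against 2.0, SE = √(5.0/120) = 0.204 and power = Φ(4.90 − 1.96) = 99.8% (stated: 99.9%). Both are within 2 points of the plan, so its figures fit an unadjusted count comparison.

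**2. Strata in a logistic model.** The plan gives no cut-point, so four are shown, with event rates P(X ≥ c) from Poisson means 3.0 and 2.4. Assumed: four equally likely strata, two factors with equal odds ratio (OR), permuted blocks of 4 within strata, Wald test. There were 4,000 simulated trials per cell, with simulation error of about 0.8 points. Entries are power, unadjusted / strata-adjusted, in %.

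| Discrepancies (event rates) | OR 1.0 | OR 1.5 | OR 2.0 | OR 3.0 |
|---|---|---|---|---|
| ≥1 (95.0% vs 90.9%) | 20.1 / 20.3 | 20.5 / 21.0 | 20.0 / 20.9 | 20.0 / 21.2 |
| ≥2 (80.1% vs 69.2%) | 49.2 / 49.7 | 47.4 / 48.9 | 49.6 / 51.7 | 49.1 / 54.0 |
| ≥3 (57.7% vs 43.0%) | 61.0 / 61.6 | 62.3 / 64.2 | 62.2 / 65.8 | 62.3 / 68.1 |
| ≥4 (35.3% vs 22.1%) | 61.2 / 61.4 | 62.1 / 63.0 | 60.2 / 62.6 | 63.0 / 67.5 |

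The gain is about 0 to 4 points up to OR 2.0. OR 3.0 per factor means 3 × 3 = 9-fold odds between extreme strata, for which the documents give no support. Unadjusted type I error at ≥3 is 4.3% (OR 2.0) and 3.6% (OR 3.0) in blocks, and 4.5% and 5.1% with simple randomisation. It is not inflated.

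**3. Strata in a count model.** Assumed rate ratio 1.5 per factor. The stratum rates are then 1.92, 2.88, 2.88 and 4.32 (mean 3.0). Between-stratum variance is (1.08² + 0.12² + 0.12² + 1.32²)/4 = 0.734, so total variance over mean is 1 + 0.734/3 = 1.245, and √1.245 = 1.116.

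- *Balanced strata, model-based Poisson variance:* the SE of the log rate ratio is √(1/360 + 1/288) = 0.0791. Power is Φ(0.2231/0.0791 − 1.96) = 80.6%, and adjusting gains about 0.
- *Balanced strata, empirical variance:* the reported SE rises to √(0.00625 + 2 × 0.0816/120) = 0.0872, where 0.0816 = 0.734/3.0². Power is Φ((0.2231 − 1.96 × 0.0872)/0.0791) = 74.5%, against about 81% adjusted. Type I error is 2[1 − Φ(1.96 × 1.116)] = 2.9%.
- *Simple randomisation, unadjusted plain Poisson:* type I error is 2[1 − Φ(1.96/1.116)] = 7.9%.

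Simulation agrees: about 81%, 74–75% and 8%.

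**4. Baseline MUSE and SF-12.** Assumed difference 0.3 SD; two-sided 5% noncentral t. Against the 30-day score alone, the SE is multiplied by √(1 − r²) with baseline as covariate and by √(2(1 − r)) for a change score.

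| Power | r = 0.3 | r = 0.5 | r = 0.7 |
|---|---|---|---|
| 30-day score only, 120 per arm | 64% | 64% | 64% |
| Baseline as covariate, 120 per arm | 68% | 76% | 90% |
| Change score, 120 per arm | 50% | 64% | 85% |
| 30-day score only, 96 per arm | 54.3% | 54.3% | 54.3% |
| Baseline as covariate, 96 per arm | 58.2% | 66.6% | 82.5% |

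The 96 per arm is 0.8 × 120, assuming 20% are not interviewed. Below r = 0.5 a change score is weaker than ignoring baseline.

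**The case against.** **The stratification may not be live.** Its sentence points to a Figure 2 and a Section 4.e.5. In the supplied text Figure 2 is the PDF version of the tool, and no Section 4.e.5 appears. The non-response paragraph still speaks of three groups in a two-arm trial. This stands, so the first step is to confirm whether stratification is used.

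**An unadjusted primary analysis is a legitimate prespecified choice, and nothing shows that the strata are prognostic.** This largely stands for the logistic test. The pilot's remark that further discrepancies were most often duplicates across VA Boston and another VA facility makes an effect plausible but gives no size.

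**The MUSE figures rest on an assumed effect, assumed correlations and a normal model for a 0-to-8 score.** True. They show direction and range only.

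Some stronger readings are not supported:

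- A reader might infer that leaving out the strata invalidates the primary test. For the logistic model it does not. Only a plain Poisson model with simple randomisation inflates type I error here, and the plan names no such model.
- A reader might conclude that strata adjustment gains nothing in a count model. That holds only with balanced strata and model-based variance.
- A reader might say that the baseline scores go unused, or that the strata are barred. The documents merely do not name them. The bivariate associations, sensitivity analyses and drop-out model are open-ended and could include them.
- A reader might take the baseline scores as contaminated. Section 3 is explicit that baseline comes first, and the Human Subjects text is a summary that joins the two events with a simple conjunction. Contamination is possible, not shown.

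**Conclusion.** The point holds as one of efficiency and unfinished specification, not of validity. If the stratification is in use, both described models should carry it. For the logistic test the benefit is nil if the strata are not prognostic and about 0 to 4 points of power up to an assumed OR of 2.0. For a count model at an assumed rate ratio of 1.5 per factor, it is about 0 points with balanced strata and model-based variance and about 6 to 7 points with empirical variance. Under simple randomisation, an unadjusted plain Poisson test would have about 8% type I error.

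The larger gain is in MUSE and SF-12: about 4 to 26 points at 120 per arm, conditional on the assumed 0.3 SD and correlations of 0.3 to 0.7. That gain depends on the baseline being measured before the arm is known, so the conflict between Section 3 and Human Subjects must be reconciled whatever is decided about the strata.

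The choice between a count and a logistic outcome is a separate matter and is not settled here.

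**What to change.** 1. Confirm that randomisation is stratified on the two factors and correct the cross-references, or delete the sentence.
2. If it is in use, include both factors as prespecified terms in the primary and the inverse-probability-weighted models, whichever outcome model is settled on. Report the unadjusted result as a sensitivity analysis. If the model is logistic, show a standardised risk difference beside the conditional odds ratio.
3. State that 30-day MUSE and SF-12 are each analysed with their baseline score as covariate, not as change scores.
4. Reconcile Section 3 and Human Subjects so that the baseline interview precedes randomisation and disclosure of the arm.
5. Optional and minor: name the sensitivity covariates in advance for expected prognostic value, not for observed imbalance.

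The cost is protocol and SAP wording, since the baseline scores and, if stratification is used, the strata are already collected. If the interview is in fact held after randomisation, the visit order changes too. One side effect is that the odds ratio becomes conditional on the strata and its reported SE rises (0.262 to 0.283 at three or more discrepancies, strata OR 3.0). The standardised risk difference loses no precision: its SD across simulations is 0.060 adjusted against 0.064 unadjusted with simple randomisation, and 0.061 for both in blocks.
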